**Date of the document: 10/02/2017**

**Background:** The transition to long-term care facility can be a stressful and emotional event for the elderly. The evidences showed that the prevalence of depression and the cognition impairment were higher in the institutionalized elderly than the community dwelling elderly. It could affect the quality of life of the elderly and increase risk of mortality.

**Purpose:** The aim of the study is to evaluate the effect of outdoor activities and sunlight exposure on depression, cognitive function, and quality of life among institutionalized elderly.

**Method:** The design is a randomized control trial. Participants will be randomly allocated to experimental or control groups by block randomization. In the experimental group, participants will be encouraged to reduce time spent on bed and bedroom. From 7:00 AM to 5:00 PM, nurses, nurse aids or family will take participants outdoors and exposure their face, hands or arm to sunlight for 15-30 minutes a day, five days a week for three months (if the UV index is over 8 according to the forecast of Center Weather Bureau, the participants will be asked to stay inside). In the control group, the participants will receive routine care. They will neither be encouraged to stay outdoors nor limit the chance to exposure to sunlight. Depression (measured by GDS-15), cognition (measured by SPMSQ), and quality of life (measured by EQ-5D) will be measured at baseline and at 3 months. Data were analyzed using SPSS 17.0 statistical software for all randomized participants. The Chi square test was used to test for homogeneity of demographic data between experimental and control group. Two-way ANOVA was used to test for differential changes in depression, cognitive function, and quality of life.

**Expected outcome:** The expected benefit of the research is to improve the depression, cognitive function, and quality of life of the institutionalized elderly.

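### Does a high-UV stay-inside rule written only for the experimental arm undermine the comparison with routine care?

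*Protocol*

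**What the plan says.** Everything relevant is in the Method paragraph of the Protocol.

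- **Experimental schedule.** "From 7:00 AM to 5:00 PM, nurses, nurse aids or family will take participants outdoors", with sunlight on the skin for "15-30 minutes a day, five days a week for three months".
- **Exception.** A parenthesis attached to that same sentence reads "if the UV index is over 8 according to the forecast of Center Weather Bureau, the participants will be asked to stay inside". Nothing is said about make-up days.
- **Second experimental component.** Separately, "participants will be encouraged to reduce time spent on bed and bedroom". The UV rule does not suspend this.
- **Control arm.** Routine care, described as "They will neither be encouraged to stay outdoors nor limit the chance to exposure to sunlight". No UV condition is attached.
- **Measurements.** "Depression (measured by GDS-15), cognition (measured by SPMSQ), and quality of life (measured by EQ-5D) will be measured at baseline and at 3 months". Outdoor or sunlight time is not named.
- **Analysis set.** The data are to be analyzed "for all randomized participants".

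**The concern.** The Purpose names outdoor activity and sunlight as the exposure of interest. On a high-UV day, experimental participants are asked to stay in, while controls may go out if their routine allows it. The arms then differ by nothing, or in the wrong direction, on the variable under study. Five outings a week may also not be achieved.

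Because the listed measurements are only the three outcome scales, the contrast delivered could not be recovered from them. A null result might mean that sunlight does not help, or that the arms hardly differed in sunlight. If high-UV days were common, the loss of power could be large.

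**Working it through.** **Inputs from the Protocol (Method).** Five sessions a week, 15 to 30 minutes each, for three months. Taking three months as 13 weeks (an assumption) gives 5 × 13 = 65 planned sessions.

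**Inputs the Protocol does not give.** The share f of days with forecast UV over 8, control outdoor minutes c, whether missed days are rescheduled, the sample size and the power. There is therefore no stated figure to reproduce, and everything numerical below is illustration.

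**Step 1: do the statements conflict?** The schedule and the UV rule stand in one sentence, and the rule is an express exception to the schedule. The control sentence describes a comparator on which the trial imposes nothing. A schedule with a stated exception, set against unrestricted routine care, is coherent.

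**Step 2: a single high-UV day.** Planned experimental exposure is 0 and control exposure is c ≥ 0, so the sunlight contrast is 0 − c = −c. It is zero if controls also stay in and negative only if they go out. The text permits control outings but does not show that they occur.

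**Step 3: sessions delivered.** Without make-up: 65(1 − f). With make-up in a seven-day week: 13 × E[min(5, X)], where X ~ Binomial(7, 1 − f) and days are independent.

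| Assumed f | No make-up | With make-up | Weeks in which 5 days are possible |
|---|---|---|---|
| 0 | 65 | 65 | 100% |
| 0.1 | 58.5 | 64.6 | 97% |
| 0.2 | 52 | 62.6 | 85% |
| 0.3 | 45.5 | 58.3 | 65% |
| 0.5 | 32.5 | 44.6 | 23% |

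Five days out of seven leave room for two high-UV days a week. The text neither provides for nor excludes using that room. If high-UV days cluster, rescheduling recovers less than the table shows.

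**Step 4: mean contrast on scheduled days, no make-up.** This is m(1 − f) − c for sessions of m minutes.

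- f = 0.2, c = 5: 15 × 0.8 − 5 = 7 minutes, and 30 × 0.8 − 5 = 19 minutes.
- f = 0.5, c = 5: 2.5 and 10 minutes.
- f = 0.5, c = 10, m = 15: 7.5 − 10 = −2.5 minutes.

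The rule accounts only for the part m·f. At f = 0.2 that is 3 minutes of 15, or 6 of 30; the other 5 minutes are ordinary control exposure, present with or without the rule. For the average contrast to reverse, c must exceed m(1 − f). With m = 15 and f = 0.2, controls would have to average more than 12 minutes a day.

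**Step 5: power.** Suppose 80% power at full contrast, two-sided 5%, and a response proportional to sessions delivered. Power is then Φ(2.80 × (1 − f) − 1.96), which gives 71%, 61%, 50% and 29% at f = 0.1, 0.2, 0.3 and 0.5.

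The arithmetic is right, but no input comes from the Protocol and the result depends heavily on them. At f = 0.3 with make-up, the delivered share is 58.3/65 = 0.897, and Φ(2.80 × 0.897 − 1.96) = Φ(0.55), about 71% rather than 50%. The model also gives no weight to the bed-and-bedroom component, which continues on high-UV days. These figures cannot be quoted as this trial's loss of power.

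**The case for a change.** The strongest reply is that this is not a detail for a statistical analysis plan. Which arm a rule covers, and what is recorded during the intervention, are protocol matters, and no analysis can use exposure that was never collected. The aim is stated in terms of sunlight, so readers will want to know how much each arm received. Rescheduling is not promised, and even with it, five days would be possible in only 65% of weeks at an assumed f of 0.3.

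Part of this stands. The listed measurements do not allow a null result to be divided into failed delivery and absence of effect. The words used for those who stay inside could also be read as covering both arms, although their place in the experimental sentence, and the statement that controls are not limited, point to the experimental arm.

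The rest does not carry the point. The measurement sentence names the outcomes and does not say that nothing else is recorded; a session log could sit in operational material. Extending the rule to controls would alter routine care and contradict the control sentence. Logging outdoor time in the control arm could make staff more aware of it and so narrow the contrast. The question the trial can answer, whether offering this programme improves the outcomes compared with routine care, does not need an exposure measure.

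**Conclusion.** No change is called for. The passages are compatible: an outdoor programme with a stated exception is compared with routine care, and the trial accepts some lost contrast on excepted days. That is a fair trade-off. Followed as written, the comparison of all randomized participants is unbiased for the effect of the programme, exception included.

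The cost is possible dilution of the sunlight part of the intervention. Its size cannot be derived from the document: it is nil if no day exceeds the threshold, and it grows with the frequency of such days and with control outings, neither of which is given. The illustrations rest on a 13-week period, independent days and assumed values of f and c; the power figures further assume 80% baseline power and a proportional response.

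What remains is optional. The wording could name the arm to which the rule applies and say how the five-day schedule works on such days, and caregivers could note sessions delivered. The clinical rule itself is for the investigators. None of this corrects a rule that would give a wrong result.

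### The two-way ANOVA for change in twice-measured scores names neither a within-person term nor the baseline as covariate; it loses power on one reading and some precision on the other

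*Protocol*

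**What the plan says.** The relevant text is the Method paragraph of the Protocol.

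- **Design:** "Participants will be randomly allocated to experimental or control groups by block randomization".
- **Outcomes:** GDS-15, SPMSQ and EQ-5D. All three "will be measured at baseline and at 3 months", so each participant contributes two scores per outcome.
- **Efficacy analysis:** "Two-way ANOVA was used to test for differential changes in depression, cognitive function, and quality of life". No other analysis of the outcomes is named.
- **Analysis set and software:** "Data were analyzed using SPSS 17.0 statistical software for all randomized participants".
- **Other test:** "The Chi square test was used to test for homogeneity of demographic data between experimental and control group". This compares demographic data and adjusts no outcome.

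The paragraph mentions no subject term, repeated-measures label, mixed model or baseline covariate. It gives no significance level, sample size, power, SD or correlation.

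**The concern.** A test of differential change between two groups measured twice is a test of the group-by-time interaction. An ordinary two-way ANOVA assumes that all observations are independent, and two scores on the same scale from the same person are not. The sentence therefore allows two readings.

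1. **Ordinary two-way ANOVA (literal).** The between-person variation that cancels out of a change stays in the error term. With positive correlation, the standard error of the interaction is overstated and the test rejects too rarely.
2. **Repeated-measures (mixed) ANOVA.** With two time points, the interaction test is the same as a t-test on change scores. It is valid and unbiased under randomisation, but it fixes the baseline slope at 1 instead of estimating it. That costs precision, and for a given chance imbalance at baseline the estimate carries regression to the mean.

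The point estimate is the same under both readings; only the standard error differs. This is the sole stated efficacy test and it serves all three outcomes, so a real effect could be missed on each of them.

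**Working it through.** The Protocol states no sample size, power or significance level, so there is no figure of its own to reproduce.

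**Inputs from the Protocol:** two randomised arms, two measurements per person, and a two-way ANOVA for change.

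**Assumptions:** n per arm with equal arms; the same SD at both times; two-sided 5%; correlation rho between a person's two scores of 0.3, 0.5, 0.7 or 0.9.

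**Formulas**

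- True variance of the difference in mean change: 4·SD²·(1−rho)/n.
- Variance that the ordinary two-way ANOVA assumes: 4·SD²/n.
- Ratio of assumed to true standard error: 1/√(1−rho).
- True type I error of the literal test: 2·[1 − Φ(1.96/√(1−rho))].
- ANCOVA variance (large sample): 2·SD²·(1−rho²)/n.
- Change-score variance relative to ANCOVA: 4(1−rho) / [2(1−rho)(1+rho)] = 2/(1+rho).
- Power when ANCOVA has 80% (noncentrality 1.96 + 0.84 = 2.80): repeated measures Φ(2.80·√((1+rho)/2) − 1.96); literal Φ(2.80·√((1+rho)/2) − 1.96/√(1−rho)).

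**Worked case, rho = 0.5.** The standard-error ratio is 1/√0.5 = 1.414. The literal test's type I error is 2·[1 − Φ(2.772)] = 0.0056. The variance ratio is 2/1.5 = 1.333. Repeated-measures power is Φ(2.426 − 1.960) = 0.68, and literal power is Φ(2.426 − 2.772) = 0.37.

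| rho | 0.3 | 0.5 | 0.7 | 0.9 |
|---|---|---|---|---|
| Literal: SE overstated by | 20% | 41% | 83% | 216% |
| Literal: true type I error | 1.9% | 0.6% | 0.03% | about 0 |
| Repeated measures: variance relative to ANCOVA | 1.54 | 1.33 | 1.18 | 1.05 |
| Repeated measures: SE larger than ANCOVA by | 24% | 15% | 8% | 3% |
| Power, ANCOVA | 80% | 80% | 80% | 80% |
| Power, repeated measures | 62% | 68% | 73% | 78% |
| Power, literal | 47% | 37% | 16% | below 1% |

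**Simulation check** (20,000 trials per setting, an assumed 40 per arm). With no effect, the literal interaction test rejected in 1.9%, 0.7% and 0.04% of trials at rho 0.3, 0.5 and 0.7. Repeated measures and ANCOVA stayed between 4.8% and 5.3%. With an assumed effect of 0.5 SD, power for literal / repeated measures / ANCOVA was 0.32 / 0.46 / 0.63, 0.29 / 0.60 / 0.72 and 0.25 / 0.82 / 0.87. The formulas therefore hold in a small trial.

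**Chance imbalance.** If the arms differ by 0.2 SD at baseline, the change-score estimate is shifted by an expected (1−rho)·0.2 SD, that is 0.14, 0.10, 0.06 or 0.02 SD. Averaged over randomisations the shift is zero.

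**Group main effect.** In the same literal ANOVA, the test of the group main effect errs the other way. Its type I error is 2·[1 − Φ(1.96/√(1+rho))], or 8.6%, 11.0%, 13.3% and 15.5%. This is not the effect that a test of differential change points to, but it is a further reason to name the tested effect.

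**The case against.** The strongest reply has four parts.

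- **Omitted detail.** Model terms are commonly left to a statistical analysis plan, and one may exist. A missing subject term alone would be a weak point. However, the Protocol does fix a method. A later plan could settle which reading applies, but it would not make the change-score test as efficient as ANCOVA.
- **Shorthand.** The label may simply stand for a two-way mixed ANOVA, and the reference to changes suggests within-person comparison. This is plausible, and the largest losses above belong only to the literal reading. If repeated measures was meant, the analysis is valid and the point is one of efficiency, small when rho is high.
- **Unanchored size.** This stands. The Protocol gives no rho, SD or n, so the loss can only be shown as a range. The direction is firmer: the literal interaction test is conservative for any positive rho, and the large-sample variance of ANCOVA is smaller than that of the change score for any rho from 0 up to 1.
- **Small samples.** Estimating the slope inflates the ANCOVA variance by about 1 + 1/(2n−4). At an assumed 30 per arm this is 1 + 1/56 = 1.018, so ANCOVA is marginally worse only where 2/(1+rho) < 1.018, that is above rho of about 0.965. This does not alter the recommendation.

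**Conclusion.** The concern holds, and the sentence should be changed. If the test is run literally, the power loss is serious and grows with rho. If it is run as repeated measures, the test is sound, but its variance is 54% to 5% above that of ANCOVA over rho 0.3 to 0.9; at rho 0.5 that equals needing a third more participants for the same precision. Neither reading inflates false positives for the interaction. The sizes rest on assumed values of rho, equal variances and a two-sided 5% test. The conservatism of the literal test needs a positive correlation, which is likely for one scale in one person but is not documented. Confidence is medium, because the wording does not show which analysis was meant.

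**What to change.** Replace the ANOVA sentence with: *For each outcome, the 3-month score is compared between groups by ANCOVA with the baseline score of that outcome as covariate; the adjusted mean difference and its 95% confidence interval are reported.* A linear mixed model on both time points, with within-person covariance and a common baseline mean, is an acceptable alternative. If the two-way ANOVA is kept, state that time is a within-subject factor and that the group-by-time interaction is the test.

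The cost is one sentence of wording. SPSS fits both models, the baseline scores are already collected, and no participants are added. The change must be set before the data are analysed. The analysis sentences are in the past tense, so the sponsor should confirm whether analysis has already taken place. If it has, the stated test stays as the planned one, and ANCOVA is reported as a post hoc sensitivity analysis and labelled so.
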